3.3 Inclusion of Women and Minorities

Both men and women of all races and ethnic groups are eligible for this trial.

4. REGISTRATION AND RANDOMIZATION PROCEDURES

4.1 General Guidelines for DF/HCC Institutions

Institutions will register eligible participants in the Clinical Trials Management System (CTMS) OnCore. Registrations must occur prior to the initiation of any protocol-specific therapy or intervention. Any participant not registered to the protocol before protocol-specific therapy or intervention begins will be considered ineligible and registration will be denied.

An investigator will confirm eligibility criteria and a member of the study team will complete the protocol-specific eligibility checklist.

Regorafenib is not a drug that is prescribed by the Cutaneous Oncology team. This study's recruitment relies entirely on receiving referrals from other disease centers. Due to the fact that patients are referred from these outside disease centers (such as Sarcoma and GI) and that regorafenib may require insurance clearance and then mailing, we expect that screening and randomization may occur on the same day.

In an effort to increase accrual and more quickly identify potential participants that have been prescribed regorafenib in other departments within the Institute, COC will be utilizing an EPIC report to assist in the recruitment of participants. This report has been built in collaboration with pharmacy to identify patients that have been prescribed regorafenib within the last 7 days. This report can be run by the study team at any time. The COC study team may reach out to the prescribing physician to ask their permission to contact their patient directly to describe this research study and see if they would be interested in participating in this study.

The eligibility checklist(s) and all pages of the consent form(s) will be faxed to the ODQ at [contact]. The ODQ will (a) review the eligibility checklist, (b) register the participant on the protocol, and (c) randomize the participant. ODQ will send the randomization to the research pharmacy.

Randomization can only occur during ODQ business hours (8:30am - 5pm Eastern Time, Monday through Friday excluding holidays).

An email confirmation of the registration and/or randomization will be sent to the Overall PI, study coordinator(s) from the Lead Site, treating investigator and registering person immediately following the registration and/or randomization.

Following registration, participants may begin protocol-specific therapy and/or intervention. Issues that would cause treatment delays should be discussed with the Overall Principal Investigator (PI). If the subject does not receive protocol therapy following registration, the subject must be taken off-study in the CTMS (OnCore) with an appropriate date and reason entered.

Emergency un-blinding during the clinical trial may be required during the course of the trial to assist in the proper treatment of an AE or for regulatory reasons (e.g. for expedited safety reporting). For emergency un-blinding, the PI will need to be contacted. The PI will then send a written request (i.e. email) for an emergency un-blinding to the administrative person on call from IDS pharmacy.

4.2 Registration Process for DF/HCC Institutions

Applicable DF/HCC policy (REGIST-101) must be followed.

5. TREATMENT PLAN

This is a prospective, randomized, double-blind signal detection trial comparing placebo gel plus BPS (20% urea + DFCI approved teaching sheets + pharmacy call) to tazarotene 0.1% gel plus BPS for the prevention of HFSR in patients treated with regorafenib. Each study cycle is 28 days long.

At the time of consent for regorafenib, patients will be invited to participate, consented and enrolled. Patients may already have had their first dose of regorafenib before consenting to this study, as long as regorafenib was started less than 96 hours from first application of tazarotene. Patients will be randomized 1:1 to receive either placebo gel plus best practice standards (BPS) or BPS plus tazarotene 0.1% gel daily. The current standard of care for Regorafenib includes providing patients with oral chemotherapy teaching sheets that include a Hand Skin Foot Reaction teaching sheet, pharmacy instruction and 20% urea cream daily. Participants in both arms will have urea recommended as standard best practice standards. It is available over the counter and will not be supplied.

Patients will receive regorafenib for their malignancy per their treating medical oncology team. Regorafenib is not provided as part of this study. The study team will not be making any recommendations for dose, timing of dose, concomitant medications associated with regorafenib use or prohibited foods while on regorafenib. All patients must have a plan to be treated with dose-escalation of regorafenib based on the reDOS study. The reDOS study uses this regimen: 80mg daily for week 1, 120mg daily for week 2, 160mg daily for week 3, hold drug for week 4, and then 160mg daily for each subsequent cycle with escalation and maintenance based on tolerability. All regorafenib dose adjustments are made at the discretion of the treating medical oncology team. This study team will not make any regorafenib recommendations. Treatment with tazarotene 0.1% gel or placebo is continued daily during the week that regorafenib is held.

Outcomes will be assessed by a dermatology provider at 2-week intervals until 8 weeks, then again at week 12,

16, 20, and 24. If HFSR develops, with evidence of inflammation, patients will be treated at the discretion of the treating physician in both arms of the study.

Clinical and patient demographic factors will be collected. These will include age, gender, BMI, malignancy characteristics, smoking status, occupation, hobbies, activity level, co-morbidities, marital/relationship status, ECOG performance status, prior therapies and prior dermatologic history.

Surveys listed in the study calendar will be delivered in the clinic setting. They may be given in either paper or electronic formats. Every effort will be made to collect the surveys at the required timepoints. Missing data on the questionnaires, either an incomplete or missing survey will be documented but will not be considered a protocol deviation. Survey data will be collected at the designated clinic visits +/- a 3 days window to increase our survey return response rates. Patients may complete the surveys at home, and mail them back to the study team.

The primary endpoint is the development of grade-2 or greater HFSR within 8 weeks of starting protocol therapy. This endpoint is chosen based on its significance of this toxicity grade on ADLs and dose modification. It is the endpoint time used in the reDOS study, as it allows for 2 full cycles of therapy, one with regorafenib dose escalation and one at maximum tolerated dose. It was also chosen to minimize the risk of drop out.

5.1 Treatment Regimen

Control arm: Pharmacy teaching call, DFCI approved teaching sheets and 20% urea applied to the palms and soles in the morning with placebo gel applied in the evening.

Intervention arm: Pharmacy teaching call, DFCI approved teaching sheets and 20% urea applied to the palms and soles in the morning + tazarotene 0.1% gel, applied to the palms and soles nightly.

Both arms will receive standard chemotherapy teaching call from pharmacy as well as the DFCI approved teaching sheets in patient education handouts. No investigational or commercial agents or therapies other than those described below may be administered with the intent to treat the participant's HFSR.

5.2 Pre-Treatment Criteria

5.2.1 Cycle 1, Day 1

N/A. There are no pretreatment criteria for this study

5.2.2 Subsequent Cycles

Patients will continue topical therapy as long as the regorafenib treatment plan is not discontinued permanently.

5.3 Agent Administration

Administration – Tazarotene 0.1% gel or placebo will be applied topically every night. Those patients experiencing < grade 2 HFSR will be allowed to continue through 24 weeks. If the endpoint of grade 2 or

greater HFSR is reached, this will be treated at the physician's discretion. Please note, with participants with large hands and feet, it is permissible to dispense two 30 gm tubes of Tazarotene 1% gel/Placebo. Earlier visits for dispensing are allowed if participants run out of drug early.

Dosing – Tazarotene 0.1% gel or placebo gel will be applied at 8 pm +/- 4 hours. Urea cream, if recommended as part of BPS will be applied at 8am +/- 4 hours.

½ Fingertip unit will be applied per palm/sole (1FTU=2% BSA). 1gram of gel covers 4% BSA. 1 palm is 1%, therefore patients will be prescribed 30g per 28-day period.

Patients will document application in a drug diary. See Appendix B.

Caregiver Precautions – Tazarotene should not be dispensed by a pregnant woman. If this is required, the caregiver should wear gloves.

Missed doses should be skipped entirely.

Please refer to Appendix E: Tazarotene or Placebo Preparation Instructions

5.4 General Concomitant Medication and Supportive Care Guidelines

Concomitant use of systemic retinoids, treatment dose steroids or topical steroids for HFSR prior to the development of symptoms is prohibited. Other systemic agents for the treatment of HFSR are prohibited. Topical agents beyond that outlined as best practice standards (“BPS”) are prohibited.

Because there is a potential for interaction of Tazarotene with other concomitantly administered drugs through the cytochrome P450 system, the case report form must capture the concurrent use of all other drugs, over-the-counter medications, or alternative therapies. The Overall PI should be alerted if the participant is taking any agent known to affect or with the potential to affect selected CYP450 isoenzymes. Appendix C presents guidelines for identifying medications/substances that could potentially interact with the study agent(s).

5.5 Criteria for Taking a Participant Off Protocol Therapy

Duration of therapy will depend on individual response, evidence of HFSR development, progression and tolerance of tazarotene. In the absence of treatment delays due to adverse event(s), treatment may continue for up to 24 weeks or until one of the following criteria applies:

- HFSR grade >/=2 develops and fails to respond to supportive interventions at the treating physician discretion
- Intercurrent illness that prevents further administration of treatment
- Unacceptable adverse event(s)
- Participant demonstrates an inability or unwillingness to comply with the topical medication regimen

and/or documentation requirements

- Participant decides to withdraw from the protocol therapy
- General or specific changes in the participant's condition render the participant unacceptable for further treatment in the judgment of the treating investigator

Participants will be removed from the protocol therapy when any of these criteria apply. The reason for removal from protocol therapy, and the date the participant was removed, must be documented in the case report form (CRF). Alternative care options will be discussed with the participant.

When a participant is removed from protocol therapy and/or is off the study, the relevant Off-Treatment/Off-Study information will be updated in OnCore.

Participants may be removed from the protocol therapy, but remain on study for the duration of the follow up period.

5.6 Duration of Follow Up

Participants will be followed for a minimum of 28 days (4 weeks) after removal from protocol therapy or until death, or regorafenib discontinuation with resolution of HFSR, whichever occurs first. Participants who do not develop HFSR who discontinue regorafenib do not require follow up after removal from protocol therapy. Participants removed from protocol therapy for unacceptable adverse event(s) will be followed until resolution or stabilization of the adverse event. Once removed from protocol therapy, study assessments (PE, vitals, questionnaires) will take place at visits paired with medical oncology SOC visit schedule.

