13.1 Study Design/Endpoints

Endpoints

The primary endpoint will be the proportion of patients in each arm who develop grade-2 or higher HFSR within the first 8 weeks of protocol therapy. A parallel secondary endpoint will be the proportion of patients in each intervention arm who develop HFSR of any grade.

Efficacy Analysis

Primary Endpoint: For each comparison, the proportion of patients with grade-2 or higher HFSR will be compared between placebo gel plus BPS and tazarotene gel plus BPS using a two-group chi-squared test. The difference between the two proportions will be summarized with a 90% confidence interval.

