13.6.2 Evaluation of the Primary Efficacy Endpoint

Data will be analyzed based on intent-to-treat.

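### After permanent gel removal, Section 5.6 replaces the dated HFSR grading and surveys with oncology visits of unstated frequency, and required follow-up can end before the Week 8 primary endpoint

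*Combined protocol and SAP*

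**What the plan says.** Section 5 sets the normal schedule: "Outcomes will be assessed by a dermatology provider at 2-week intervals until 8 weeks", then at Weeks 12, 16, 20 and 24. The Section 10 calendar puts the questionnaires on the same dates. Section 13.5 gives the dermatology tools a one-week recall and the PSS a 4-weekly schedule.

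Section 13.1 defines the primary endpoint as "the proportion of patients in each arm who develop grade-2 or higher HFSR within the first 8 weeks of protocol therapy", and Section 13.6.2 adds: "Data will be analyzed based on intent-to-treat". Section 13 has no rule for a patient who is not graded to Week 8.

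Section 5.6 governs patients removed from protocol therapy:
- **Visits:** "Once removed from protocol therapy, study assessments (PE, vitals, questionnaires) will take place at visits paired with medical oncology SOC visit schedule".
- **Length:** "Participants will be followed for a minimum of 28 days (4 weeks) after removal from protocol therapy", ending sooner on death or when regorafenib is stopped and HFSR has resolved.
- **No HFSR and regorafenib stopped:** "Participants who do not develop HFSR who discontinue regorafenib do not require follow up after removal from protocol therapy". Section 5.2.2 ties the gel to regorafenib: "Patients will continue topical therapy as long as the regorafenib treatment plan is not discontinued permanently".
- **Removal for toxicity:** "Participants removed from protocol therapy for unacceptable adverse event(s) will be followed until resolution or stabilization of the adverse event".

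Reasons for removal in Section 5.5 include grade 2 or higher HFSR that does not respond to supportive care, unacceptable adverse events, non-compliance and patient choice.

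**The concern.** An intent-to-treat comparison of 8-week event proportions needs every randomised patient's HFSR status to Week 8, whether or not the gel is still in use. Section 5.6 ties the intensity and length of observation to staying on gel. A patient who stops gel at Week 2 but continues regorafenib remains at risk of grade 2 or higher HFSR, yet leaves the 2-weekly dermatology grading.

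The survey problem is different. Unresponsive grade 2 or higher HFSR is itself a reason for removal. Those patients already count as primary events, but they leave the survey dates when their skin-related quality of life is of most interest. With one-week recall, a later survey cannot recover a missed date. The comparisons on Skindex-16, DLQI, HFS-14 and PSS could then rest on patients measured at different times for reasons linked to outcome.

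**Working it through.** **1. The plan's own figures.** Inputs from Section 13.2: 35 per arm, 50% v 25%, one-sided 0.10, futility look at 14 per arm.

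Fixed-design power = Φ{[d√n − z√(2p̄(1−p̄))] / √(p₁(1−p₁)+p₂(1−p₂))}, with d = 0.25, p̄ = 0.375 and z = 1.2816.
- This is Φ{(1.479 − 0.878)/0.661} = 0.818, against 80% stated.
- With the futility look (bivariate normal), power is 0.790.
- The null stopping probability is Φ(0.107) = 0.543, as stated.

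The design reproduces.

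**2. Where required follow-up ends.** Removal on Day d gives a minimum to Day d + 28. This falls before Day 56 whenever d < 28.

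**3. Scheduled dates lost after removal at Week w.** Inputs:
- Primary gradings: Weeks 2, 4, 6, 8.
- Skindex-16, DLQI and HFS-14: Weeks 2, 4, 6, 8, 12, 16, 20, 24 (8 dates).
- PSS at 4-week intervals: Weeks 4, 8, 12, 16, 20, 24 (6 dates). The calendar lists all tools together, but Sections 1.3 and 13.5 make the PSS 4-weekly.

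Each cell counts the dates after w, then (in brackets) those also after w + 4.

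| Removed at | Minimum ends | Primary gradings | Skindex-16, DLQI, HFS-14 | PSS |
|---|---|---|---|---|
| Week 2 | Week 6 | 3 (1) | 7 (5) | 6 (5) |
| Week 4 | Week 8 | 2 (0) | 6 (4) | 5 (4) |
| Week 6 | Week 10 | 1 (0) | 5 (4) | 5 (4) |
| Week 8 | Week 12 | 0 (0) | 4 (3) | 4 (3) |

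The first number is dates moved to oncology visits; the bracketed number is dates with no required follow-up at all. For an HFSR-free patient who stops regorafenib, none of the remaining dates is required.

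**4. What one uncaptured event would do.** 1/35 = 2.9 percentage points, which is 11% of the 25-point difference (50% v 25%) or 19% of a 15-point difference (40% v 25%). At the interim, 7 v 7 events gives Z = 0 and p = 0.500, so the trial stops (threshold 0.458). With 7 v 6, Z = −0.379 and p = 0.352, so it continues. This is true of any missed event in a trial this size; it does not measure the defect.

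**5. Sensitivity of the primary test, on assumed rates only.** The documents give no gel-stopping rate. Suppose a fraction m stop gel before any event and a fraction u of their events is missed and counted as no event. The observed rate is then p(1 − mu). Fixed design, normal approximation:
- Equal stops with u = 1: m = 10% gives 45% v 22.5%, power 0.77; m = 20% gives 40% v 20%, power 0.71.
- No true effect (50% in both arms), stops of 15% tazarotene v 5% placebo: observed 48.75% v 46.25% (u = 0.5), rejection probability 0.14; 47.5% v 42.5% (u = 1), 0.19.
- The same stops reversed between arms: 0.07 and 0.04.

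**6. Sensitivity of the surveys, on assumed rates only.** Suppose 25% of one group goes unsurveyed in one arm, and patients with grade 2 or higher HFSR score a constant S worse. The difference between arms is S times the difference in the share of surveyed patients with such HFSR.
- At 50% v 25% (true 0.250 S): losing placebo patients with HFSR gives 0.375/0.875 − 0.25 = 0.179 S (−29%); losing placebo patients without it gives 0.500/0.875 − 0.25 = 0.321 S (+29%).
- At 40% v 25% (true 0.150 S): 0.300/0.900 − 0.25 = 0.083 S (−44%) and 0.400/0.850 − 0.25 = 0.221 S (+47%).

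Both sensitivities change sign with the assumption.

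**The case against.** The other side has a good deal to say.

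- **Events may still be recorded.** The endpoint is a CTCAE grade. All adverse events are CTCAE-graded (7.2) and entered on the case report form (7.7). They are reportable to 28 days after the last dose (7.3.2), and the off-study column of the calendar marks an adverse event evaluation. A reader might infer that later events go unseen; that is too strong. But the 28-day window has the same Week 8 shortfall. Footnote f times the off-study visit from the last regorafenib and gel dose, and the column as extracted shows no exam or questionnaire. Neither replaces 2-weekly dermatology grading.
- **Irritation mostly does not lead to removal.** Section 6 answers local irritation with reduced frequency or a hold, and assessments continue during a hold. Removal needs an unacceptable event, and those patients are followed to resolution or stabilization. A reader might infer that tazarotene's irritancy, against an ultrasound-gel placebo, biases the result in its favour. The documents show no imbalance.
- **Section 5.6 reschedules; it does not cancel.** Oncology visit frequency is not stated, 28 days is a minimum, pairing does not exclude a dermatologist, and Section 5 allows mailed and electronic surveys with every effort at collection. Sparse data is therefore a possible inference but not shown. What stands is that the dates are no longer required.
- **Burden and relevance.** Pairing visits spares ill, referred patients. HFS-14 says little about someone off regorafenib who never had HFSR. This is fair, and it limits the fix.

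**Conclusion.** The gap is in the text: after permanent gel removal the protocol stops requiring the dated grading and surveys that its intent-to-treat and quality-of-life comparisons use.

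For the primary endpoint it is narrow. It concerns mainly event-free patients off gel and still on regorafenib before Week 8, and the 28-day minimum falls short only for removal before Week 4. For the surveys it is wider, because removal for unresponsive HFSR makes survey timing depend on outcome.

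The date counts follow from the documents. The power, error-rate and survey-bias figures rest on assumed stopping and loss rates and show only that the effect could run either way. The number affected, any imbalance between arms, and the sign and size of any bias cannot be determined. A claim of demonstrated bias, or of a compromised primary result, would go beyond the documents. This is a cheap improvement worth making.

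**What to change.** Amend Section 5.6 so that every randomised patient who is alive and consenting keeps the following after gel removal:

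- **(a)** HFSR grading at whichever of Weeks 2, 4, 6 and 8 remain, at minimum while on regorafenib.
- **(b)** The Section 10 questionnaire dates (PSS 4-weekly), by the mail or electronic routes Section 5 already allows, at minimum for patients still on regorafenib or with HFSR.

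Exam and vitals after Week 8 may follow the oncology schedule. Report missing gradings and surveys by arm and HFSR status.

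Cost: amendment wording, remote surveys, and at most three already scheduled gradings (Weeks 4, 6 and 8) for a patient removed at Week 2. No new staff or procedure is needed. The downside is a small visit and survey burden on patients who have stopped the gel, some of them ill.

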5.7 Criteria for Taking a Participant Off Study

Participants will be removed from study when any of the following criteria apply:

- Lost to follow-up
- Withdrawal of consent for data submission
- Death

The reason for taking a participant off study, and the date the participant was removed, must be documented in the case report form (CRF). In addition, the study team will ensure Off Treatment/Off Study information is updated in OnCore in accordance with DF/HCC policy REGIST-101.

6. DOSING DELAYS/DOSE MODIFICATIONS

Dose delays and modifications will be made as indicated in the following table(s).

Dose Modification Table:

Event	Management/Next Dose for Tazarotene/Placebo
≤ Grade 1 (mild irritation or peeling without pain or significant erythema on the non-palmoplantar skin)	No change in dose
Grade 2 (Erythema or irritation on the non-palmoplantar skin requiring intervention)	
- Decrease frequency of application to every other day.- Apply Vaseline to dorsal hands and feet prior to application of tazarotene to palms
Grade 3 (Erosions or bullae on the non-palmoplantar skin)	
- Hold tazarotene until grade ≤ 2- Apply Vaseline to dorsal hands and feet prior to application of tazarotene to palms- Decrease frequency of application to two times a week.

If drug is held, study assessments will still continue.

7. ADVERSE EVENTS: LIST AND REPORTING REQUIREMENTS

Adverse event (AE) monitoring and reporting is a routine part of every clinical trial. The following list of reported and/or potential AEs (Section 7.1) and the characteristics of an observed AE (Section 7.2) will determine whether the event requires expedited reporting **in addition** to routine reporting.

